4.1.2 SAMPLE SIZE

The sample size of the study has been based on the following assumptions:

- Virologic assumption: Early treatment with antivirals increases the proportion of patients with undetectable SARS-CoV-2 in upper respiratory tract at day 7 after therapy from 25% to 50%.
- Clinical assumption: Early treatment with antivirals increases the proportion of

patients who recover without need of mechanical ventilation and/or supplemental oxygen therapy by the day 14 after therapy from 50% to 75%.

Based on these assumptions and considering a randomization ratio 1:1:1, the sample size will be adaptively determined to achieve a power greater than 80% to show superiority of raloxifene vs placebo in terms of either one of primary endpoint and controlling the one-sided alpha below 0.025.

Sample size will be determined through the following steps:

- an interim analysis will take place when 50 patients per arm (N=150) have reached their primary endpoints (i.e. assessments available).
 - In case of efficacy of at least one treatment arm or futility of both arms (see criteria in protocol section 9.3) the study enrollment will be stopped,
 - otherwise the actual number of new patients in each arm may be blindly reassessed according to observed efficacy of the best favourable and promising arm;
- in case of continuation of the study to the final stage, it is expected to randomize on average additional 174 patients, depending on sample size reassessment and possible dropping of an ineffective treatment arm. Expected sample size will be between 250 and 450 randomized patients;
- drop-outs of randomized subjects will not be replaced.

This approach allows either to minimize the number of enrolled patients if the experimental assumptions are too conservative or to have a good power level if they are too optimistic.

Pocock's spending functions and conditional power (CP) will be used to control the type I and II errors, considering that interim analysis will be performed when half of the initial planned patients have been reached the primary endpoints (i.e. assessments available).

Bonferroni method is used to adjust for multiple endpoint vs treatment comparisons. Sample size calculation has been performed through simulation (100000 replications). The statistical software used for simulation was SAS®, Version 9.4.

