14.1.1 PRIMARY EFFICACY ENDPOINTS AND ANALYSES

1. Proportion of patients with undetectable SARS-CoV-2 at PCR at day 7 after randomization (virologic endpoint). This endpoint will be derived as below.
 - Based on Approved molecular test (PCR) result at day 7, the responses will be considered as “detectable” if PCR result is “Positive” otherwise “undetectable” if PCR result is “Negative” (Missing PCR result will be considered as missing in the main analysis).

The response (detectable / undetectable) at day 7 will be analysed using Binary logistic regression model with treatment group and pre-defined baseline factors (center, age, status and their interaction effects with treatment group). Odds ratio

will be computed for comparisons of each active treatment group versus placebo. i.e., raloxifene (60 mg) versus placebo and raloxifene (120 mg) versus placebo.

2. The proportion of patients who does not require supplemental oxygen therapy (NEWS ≤ 2) and mechanical ventilation at day 14 after randomization (clinical endpoint). This endpoint will be derived as below.

- If collected NEWS score > 2 or mechanical ventilation at day 14 result “Yes” then the response will be considered as “Required”. If collected NEWS score ≤ 2 and mechanical ventilation with result “No” then the response will be considered as “Not Required” (if both NEWS score and mechanical ventilation are missing, patient will be considered as missing).

The response (Required/ Not required) at day 14 will be analysed using Binary logistic regression model with treatment group and pre-defined baseline factors (center, age, status, baseline NEWS and their interaction effects with treatment group). Odds ratio will be computed for comparisons of each active treatment group versus placebo. i.e., raloxifene (60 mg) versus placebo; and raloxifene (120 mg) versus placebo.

For both virologic and clinical endpoint, Binary Logistic regression will be performed using PROC GENMOD in SAS® on the observed data only to estimate difference in proportions between each active treatment versus placebo and its corresponding 95% (2-sided) confidence intervals. Exponential transformation will be used to obtain the odds ratio and corresponding 95% confidence interval. P-values will be reported based on the Wald tests from Type III analyses. Bonferroni method will be considered to handle multiple treatment comparisons.

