In the SAS® procedure PROC GENMOD, a Type III analysis will be performed by adding the model options: TYPE3, DIST=BIN and LINK=LOGIT.

If the model does not converge then the following steps will be performed subsequently:

- PROC GENMOD with EXACT statement will be used.
- If the model still does not converge, then remove the factors/covariates from the model one by one (according to statistical significance) until convergence reached.
- If the model still does not converge, then perform the Fisher's exact using the SAS procedure PROC FREQ without adjusting for any pre-defined factor and covariates.

The following hypotheses will be tested:

- The null hypothesis for the virologic endpoint is that proportion of treated patients with undetectable SARS-CoV-2 at PCR at day 7 after randomization ($\pi_{RALOXIFENE}$) is lower or equal the placebo one ($\pi_{PLACEBO}$). Two sets of null and alternative hypotheses are provided, one for each treatment dosage:

$$H_{01-60mg}: \pi_{RALOXIFENE-60mg} \leq \pi_{PLACEBO}$$

$$H_{11-60mg}: \pi_{RALOXIFENE-60mg} > \pi_{PLACEBO}$$

$$H_{01-120mg}: \pi_{RALOXIFENE-120mg} \leq \pi_{PLACEBO}$$

$$H_{11-120mg}: \pi_{RALOXIFENE-120mg} > \pi_{PLACEBO}$$

- The null hypothesis for the clinical endpoint is that proportion of treated patients who does not require supplemental oxygen therapy (NEWS ≤ 2) and/or mechanical ventilation at day 14 after randomization ($T_{RALOXIFENE}$) is lower or equal the placebo one ($T_{PLACEBO}$). Two sets of null and alternative hypotheses are provided, one for each treatment dosage:

$$H_{02-60mg}: T_{RALOXIFENE-60mg} \leq T_{PLACEBO}$$

$$H_{12-60mg}: T_{RALOXIFENE-60mg} > T_{PLACEBO}$$

$$H_{02-120mg}: T_{RALOXIFENE-120mg} \leq T_{PLACEBO}$$

$$H_{12-120mg}: T_{RALOXIFENE-120mg} > T_{PLACEBO}$$

Superiority of raloxifene will be established if at least one null hypothesis is rejected.

The frequency and percent will be presented by treatment and visit for both primary endpoints results.

The following figures will be produced for both primary endpoints results:

- Bar chart for Proportion of Patients with undetectable SARS-CoV-2 at PCR by treatment and visit
- Bar chart for Proportion of Patients who does not require supplemental oxygen therapy (NEWS ≤ 2) and/or mechanical ventilation by treatment and visit

The following listings will be presented:

- Listing for the Nasopharyngeal Swab Test (PCR) results
- Listing for the supplemental oxygen therapy (NEWS ≤ 2) and/or mechanical ventilation

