14.1.2 SECONDARY EFFICACY ENDPOINTS AND ANALYSES

1. Proportion of patients with undetectable SARS-CoV-2 at PCR at day 14 after randomization at day 28 after randomization. Analyses will be performed on FAS population. This endpoint will be derived as below

- Based on Approved molecular test (PCR) result, the responses will be considered as “detectable” if PCR result is “Positive” otherwise “undetectable” if PCR result is “Negative” (Missing PCR result will be considered as missing).

The response (detectable / undetectable) at day 14 and day 28 will be analysed using repeated measures logistic regression model with treatment group, visit and pre-defined baseline factors (center, age and status). Odds ratio will be computed for comparisons of each active treatment group versus placebo at each assessment day i.e., raloxifene (60 mg) versus placebo; and raloxifene (120 mg) versus placebo. Analyses will be performed on FAS population using observed data only.

2. Proportion of patients who does not require supplemental oxygen therapy (NEWS ≤ 2) and mechanical ventilation at day 7 and 28 after randomization. This endpoint will be derived as below

- If collected NEWS score > 2 or mechanical ventilation with result “Yes” then the response will be considered as “Required”. If collected NEWS score ≤ 2 and mechanical ventilation with result “No” then the response will be considered as “Not Required” (if both NEWS score and mechanical ventilation are missing, patient will be considered as missing).

The response (Required / Not Required) at day 7 and day 28 will be analysed using repeated measures logistic regression model with treatment group, visit and pre-defined baseline factors (center, age, status and baseline NEWS). Odds ratio will be computed for comparisons of each active treatment group versus placebo at each assessment day. i.e., raloxifene (60 mg) versus placebo; and raloxifene (120 mg) versus placebo. Analyses will be performed on FAS population using observed data only.

For the above two secondary endpoints, Repeated Measures Logistic regression will be performed using PROC GENMOD in SAS® on the observed data only to estimate difference in proportions between each active treatment versus placebo and its corresponding 95% (2-sided) confidence intervals. Exponential transformation will be used to obtain the odds ratio and corresponding 95% confidence interval. P-values will be reported based on the Wald tests from Type III analyses.

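### The SAP calls the estimate from its logit-link models a difference in proportions, but that estimate is a log odds ratio and no conversion is specified

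*SAP*

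**What the plan says.** For both primary endpoints, SAP 14.1.1 runs a binary logistic regression in PROC GENMOD "to estimate difference in proportions between each active treatment versus placebo", with a two-sided 95% confidence interval. The next sentence reads: "Exponential transformation will be used to obtain the odds ratio and corresponding 95% confidence interval". The model options are given as "TYPE3, DIST=BIN and LINK=LOGIT", and p-values come from Type III Wald tests.

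The virologic model contains treatment and baseline factors, described as "center, age, status and their interaction effects with treatment group". The clinical model adds baseline NEWS, also with its interaction. Table 3 in SAP 14.1 lists the factors without interactions.

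SAP 14.1.2 covers two further endpoints: undetectable virus at days 14 and 28, and no need for oxygen or ventilation at days 7 and 28. There, "Repeated Measures Logistic regression will be performed using PROC GENMOD", with the same stated purpose, the same exponentiation and the same logit link.

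If a primary model does not converge, SAP 14.1.1 moves first to the EXACT statement, then to dropping covariates, then to Fisher's exact test. No interval for a difference is named at any of these steps.

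**The concern.** The sentences in 14.1.1 cannot all describe one estimate. If exponentiating it gives an odds ratio, it is a log odds ratio. If it is a difference in proportions, exponentiating it does not give an odds ratio. Neither document supplies what would reconcile them: there is no identity link, no averaging of predicted probabilities, no delta method and no bootstrap. Protocol 9.5.2.1 specifies logistic regression and no conversion. SAP 4.4 promises 95% limits for the efficacy endpoints without a method for this one, and the list of changes in SAP 18 is silent.

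At stake is the effect size and interval reported for two primary and two secondary endpoints. A programmer who follows the text literally would print a log odds ratio in a column headed as a difference in proportions. One who notices the conflict would have to choose a conversion method that the plan does not name. Enrolment stopped at 68 patients (SAP 4.3), so interpretation will lean on estimates and intervals.

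**Working it through.** **Inputs.** The planning rates are in SAP 4.1.2: for the virologic endpoint, "upper respiratory tract at day 7 after therapy from 25% to 50" per cent; for the clinical endpoint, "supplemental oxygen therapy by the day 14 after therapy from 50% to 75" per cent. The interim look at 50 per arm is half the initial plan, which implies 100 per arm. SAP 4.3 gives 68 patients included, about 23 per arm if balanced (an assumption). I use 24 per arm so that the counts are whole numbers.

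**The plan's own figures.** The SAP gives no worked value for the treatment effect estimate. The design figures built on these rates do reproduce, and they are not in dispute. A constant two-look Pocock boundary at one-sided 0.025/4 = 0.00625 solves to 2.6964, against 2.69640 in protocol Table 1. Power for one comparison at 100 per arm, counting both looks, is 87.0%, in line with the stated figure of more than 80%.

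**Point values.** The difference is p1 − p0. The logit coefficient for two arms without covariates is ln[p1/(1 − p1)] − ln[p0/(1 − p0)].

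- Virologic: difference 0.50 − 0.25 = 0.25; coefficient ln(1) − ln(1/3) = ln 3 = 1.099.
- Clinical: difference 0.75 − 0.50 = 0.25; coefficient ln(3) − ln(1) = ln 3 = 1.099.

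A difference in proportions cannot exceed 1. In the other direction, exp(0.25) = 1.28, whereas the odds ratio is 3.00.

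**Intervals.** The standard error of the difference is √[p0(1 − p0)/n + p1(1 − p1)/n]. That of the log odds ratio is the square root of the sum of the four reciprocal cell counts. At 100 per arm with 25 and 50 responders:

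- difference: √(0.001875 + 0.0025) = 0.0661, and 1.96 × 0.0661 = 0.130;
- log odds ratio: √(1/25 + 1/75 + 1/50 + 1/50) = 0.3055, and 1.96 × 0.3055 = 0.599.

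| Patients per arm | Difference (95% CI) | Logit coefficient (95% CI) | Odds ratio (95% CI) |
|---|---|---|---|
| 100 | 0.250 (0.120 to 0.380) | 1.099 (0.500 to 1.697) | 3.00 (1.65 to 5.46) |
| 24 | 0.250 (−0.015 to 0.515) | 1.099 (−0.124 to 2.321) | 3.00 (0.88 to 10.18) |

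The clinical rates give the same rows. Predicted probabilities from the fitted logit model, with a delta-method interval, return 0.250 (0.120 to 0.380) at 100 per arm. The model can therefore deliver the difference, but only through a step that the SAP does not state.

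**General size of the gap.** The slope of the logit is 1/[p(1 − p)], which is never below 4. Without covariates, the coefficient is therefore at least four times the difference; at the planning rates it is 1.099/0.25 = 4.4 times. Any coefficient below 1 would look like a possible difference, yet the true difference would be under 0.25.

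**Interactions.** With treatment-by-factor terms and reference coding, a single treatment coefficient is a log odds ratio at the reference levels only. It is then neither a difference in proportions nor an overall log odds ratio.

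**The case against.** The wording may be no more than a careless name for the treatment contrast. For each primary endpoint, SAP 14.1.1 separately says that an odds ratio will be computed for each dose against placebo, and that odds ratio is correctly named. Table content is set by separate shells (SAP 4.2 and 9), which are not part of the documents. A reader might infer that the trial will report a wrong difference. The documents do not support that as a prediction: nothing in them says that the raw coefficient will be printed under this label, and an analyst could derive a valid difference. This part of the objection stands, so the wrong number is conditional.

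A reader might also infer that the tests or the superiority conclusion are compromised. They are not affected by this wording. The Wald tests are on the logit scale, superiority depends on rejecting a null hypothesis, and frequencies and percentages by arm and visit are planned as well. Nor do hypotheses stated as proportions require a risk difference: for two arms, an active proportion no greater than placebo is the same as an odds ratio no greater than 1.

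Finally, a value of 1.10 beside the arm percentages would be conspicuous. That protects against large coefficients, but not against those below 1.

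The objection does not remove the central point: the stated analysis cannot yield the quantity that it names, and no conversion is given.

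**Conclusion.** The defect is real, limited in reach and cheap to correct. SAP 14.1.1 and 14.1.2 label a log odds ratio as a difference in proportions. If it were tabulated as labelled, the figure at the planning rates would be 1.10 instead of 0.25, and its interval at 100 per arm would be 0.500 to 1.697 instead of 0.120 to 0.380. The harm is confined to the difference and its interval.

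The numbers assume the planning rates hold exactly and use two arms without covariates. The small-sample row also assumes roughly equal arms among the 68 patients.

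A related caution concerns the odds ratio. Its scale is right, but with the interactions in 14.1.1 a single exponentiated coefficient would not be an overall odds ratio.

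**What to change.** **Minimum.** In SAP 14.1.1 and 14.1.2, name the model estimate as the log odds ratio in place of the difference in proportions. This costs a wording change only.

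**If a risk difference is wanted.** Define it from the fitted logistic model: predict each patient's probability with treatment set to each arm in turn, average over patients, subtract, and give a delta-method or bootstrap 95% interval. Conditional exact analysis does not directly supply the predicted probabilities that this needs, and Fisher's test supplies none. For both of those fallbacks, state an unadjusted Newcombe or Miettinen-Nurminen interval. The cost is a short programming step. With 68 patients and sparse centres, the standardised difference and its interval may be unstable.

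**Odds ratio.** Obtain it from a main-effects model, which is what Table 3 in SAP 14.1 lists, or from a defined overall contrast. Do not exponentiate a single reference-level coefficient from the interaction model.

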9.5.2. Analysis of efficacy variables

9.5.2.1. Primary analyses

The proportion of subjects with undetectable SARS-CoV-2 at PCR at day 7 after randomization (virologic endpoint) and the proportion of subjects who not requires supplemental oxygen therapy (NEWS ≤ 2) and/or mechanical ventilation at day 14 after randomization (clinical endpoint) will be separately analyzed by means of logistic regression models adjusting by pre-defined factors as center, age, gender and post-menopausal status. Additional covariates may be defined in the SAP. Each treatment arm will be compared independently with the placebo.

The null hypothesis for the virologic endpoint is that proportion of treated subjects with undetectable SARS-CoV-2 at PCR at day 7 after randomization is lower or equal the placebo one ($\pi_{PLACEBO}$). Two sets of null and alternative hypotheses are provided, one for each treatment dosage:

$$H_{01-60mg}: \pi_{RALOXIFENE-60mg} \leq \pi_{PLACEBO}$$

$$H_{01-120mg}: \pi_{RALOXIFENE-120mg} \leq \pi_{PLACEBO}$$

$$H_{11-60mg}: \pi_{RALOXIFENE-60mg} > \pi_{PLACEBO}$$

$$H_{11-120mg}: \pi_{RALOXIFENE-120mg} > \pi_{PLACEBO}$$

The null hypothesis for the clinical endpoint is that proportion of treated subjects who not requires supplemental oxygen therapy (NEWS ≤ 2) and/or mechanical ventilation at day 14 after randomization is lower or equal the placebo one ($\pi_{PLACEBO}$). Two sets of null and alternative hypotheses are provided, one for each treatment dosage:

$H_{02-60mg}: T_{RALOXIFENE-60mg} \leq \pi_{PLACEBO}$ $H_{02-120mg}: T_{RALOXIFENE-120mg} \leq \pi_{PLACEBO}$ $H_{12-60mg}: T_{RALOXIFENE-60mg} > \pi_{PLACEBO}$ $H_{12-120mg}: T_{RALOXIFENE-120mg} > \pi_{PLACEBO}$

Superiority of raloxifene will be claimed if at least one null hypothesis is rejected, at interim or at final analysis according to criteria shown in section 9.3.

Sensitivity analyses will be defined in the SAP to assess the robustness of results on primary endpoints versus the presence of missing data (unexpected) and the presence of protocol deviations.

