8 STATISTICAL METHODOLOGY AND CONSIDERATIONS

8.1 ADJUSTMENTS FOR COVARIATES AND FACTORS TO BE INCLUDED IN ANALYSES

In the analysis of primary endpoints and secondary endpoints, the following factors/covariates will be considered in the Binary Logistic regression and Repeated Measures Logistic regression model as described in the SAP section 14.1

- Treatment group;
- Center;
- Age group;
- Status (Male, Female pre-menopausal status, Female post-menopausal status);
- For Clinical outcome: Baseline NEWS value.

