8.4 MULTIPLE COMPARISONS/ MULTIPLICITY

Bonferroni method is used to adjust for multiple endpoints and treatment comparisons.

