14 ANALYSES OF EFFICACY VARIABLES

14.1 EFFICACY ANALYSES

NEWS score evaluation will be performed at T0, T7, T14 and T28. NEWS score and NEWS score parameters as per collected in CRF will be provided in Listing for FAS population. Refer Appendix 3 for NEWS score.

Table 3: Summary of Analyses Strategies for efficacy endpoints:

Endpoint	Analysis set	Statistical method	Factors/Co variates	Missing data Handling	Analyses type
Virologic outcome - Proportion of patients with undetectable SARS-CoV-2 at PCR at day 7 after randomization.	FAS	Binary Logistic regression	Treatment, center, age and status	Missing data will not be imputed	Primary analysis
Virologic outcome - Proportion of patients with undetectable SARS-CoV-2 at PCR at day 7 after randomization.	PP	Binary Logistic regression	Treatment, center, age and status	Missing data will not be imputed	Sensitivity analysis
Clinical outcome - Proportion of patients who does not require supplemental oxygen therapy (NEWS ≤2) and/or mechanical ventilation at day 14 after randomization.	FAS	Binary Logistic regression	Treatment, center, age, status and baseline NEWS	Missing data will not be imputed	Primary analysis
Clinical outcome - Proportion of patients who does not require supplemental oxygen therapy (NEWS ≤2) and/or mechanical ventilation at day 14 after randomization.	PP	Binary Logistic regression	Treatment, center, age, status and baseline NEWS	Missing data will not be imputed	Sensitivity analysis

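### The p-values, Bonferroni wording and model terms in SAP 14.1.1 do not match its own four one-sided hypotheses, SAP 8.4 or Table 3; align them before unblinding

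*SAP*

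**What the plan says.** **Hypotheses and claim.** SAP 14.1.1 asks for odds ratios of 60 mg and of 120 mg versus placebo. For each endpoint it states two one-sided null hypotheses, so four in all. "Superiority of raloxifene will be established if at least one null hypothesis is rejected". SAP 4.1.2 describes the design as "controlling the one-sided alpha below 0.025".

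**P-values and multiplicity.** Section 14.1.1: "P-values will be reported based on the Wald tests from Type III analyses. Bonferroni method will be considered to handle multiple treatment comparisons". Section 8.4: "Bonferroni method is used to adjust for multiple endpoints and treatment comparisons". SAP 4.1.2 agrees with 8.4. The SAP prints no per-test level. Protocol 9.3, Table 1, prints 2.69640 for the interim and the final analysis, and protocol 9.5.2.1 ties the superiority claim to that section. SAP 4.3 and 18 cancel the interim because enrolment stopped at 68 patients; neither mentions the boundary.

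**Model.** Section 14.1.1 gives the virologic model as treatment plus "center, age, status and their interaction effects with treatment group"; the clinical model adds baseline NEWS and its interaction. Table 3 lists "Treatment, center, age and status" for the virologic endpoint. Protocol 9.5.2.1 has the models "adjusting by pre-defined factors as center, age, gender and post-menopausal status". Section 18 declares neither the interactions nor the narrower Bonferroni wording.

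**If the model does not converge.** Section 14.1.1 goes first to exact logistic regression, then to removing terms one at a time by statistical significance, then to Fisher's exact test.

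**The concern.** The superiority claim is decided in 14.1.1, and an analyst following it has three choices to make that the SAP should already have made: which test decides, over how many hypotheses alpha is split, and which terms are in the model. SAP 4.4 places the final analysis after unblinding, so any choice left open can be made with the treatment codes in view. Stopping early does not make this moot. The any-one-of-four rule still stands, and at the planned effects in both doses a four-way Bonferroni rule would succeed in about 48–57% of simulated trials of 68 patients.

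**Working it through.** **Inputs from the documents.** One-sided alpha 0.025, rates 25% to 50% (virologic) and 50% to 75% (clinical), allocation 1:1:1 (SAP 4.1.2); four hypotheses (SAP 14.1.1); boundary 2.69640 with the interim at 50% (protocol Table 1); 68 patients (SAP 4.3). **Assumed:** arms of 22/23/23 or 23/23/22, no missing outcomes, and a range of correlations between endpoints. The number of centres is not given.

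**1. Reproduce the boundary.** Solve P(Z1 > c or Z2 > c) = a for two looks with correlation √0.5.
- a = 0.025/4 = 0.00625 gives c = 2.6964, the protocol's figure.
- a = 0.025/2 = 0.0125 gives 2.449; a = 0.025 gives 2.178.

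So the design splits alpha over all four hypotheses. With a single look, the critical value is 2.498 at 0.00625 and 2.241 at 0.0125.

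**2. Degrees of freedom.** Treatment has three levels, so the Type III test of treatment has 3 − 1 = 2 df and no sign. As an illustration, at 23 per arm with both doses worse than placebo (25% against 50%), an unadjusted 2-df Wald test at 0.05 is significant in about 38% of trials. The one-sided contrasts at 0.00625 reject in about 0%.

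**3. Familywise error, any of four.** Bonferroni bounds: doses only, 4 × 0.0125 = 5%; four-way, 4 × 0.00625 = 2.5%; at 2.69640, 4 × 0.0035 = 1.4%.

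| Setting | z > 2.241 (doses only) | z > 2.498 (four-way) | z > 2.69640 |
|---|---|---|---|
| Normal theory, dose correlation 0.5, endpoint correlation 0 to 0.9 | 3.3–4.6% | 1.7–2.4% | – |
| 68 patients, unadjusted pooled z | 4.2–4.5% | 2.4–2.6% | 1.1–1.2% |
| 68 patients, unadjusted Wald | 2.7–3.3% | 1.2–1.4% | 0.7% |
| Adjusted main-effects Wald, 3–6 centres assumed | 4.2–5.1% | 1.8–2.3% | 0.8–1.1% |
| The same, 10 centres assumed | 6.2% | 2.9% | 1.4% |

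**4. Change of verdict.** This is the share of trials whose largest of the four z values lies between 2.241 and 2.498. In the unadjusted analyses at the planned rates it is about 12–15% if both doses work and 11–14% if one does.

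**5. Model size with C centres.** Age is taken as one term, status as three levels and NEWS as linear.
- Virologic, main effects: 1 + 2 + (C − 1) + 1 + 2 = C + 5.
- Interactions add 2 × [(C − 1) + 1 + 2] = 2C + 4, giving 3C + 9.
- The clinical model adds 1 to the main-effects count and 1 + 2 = 3 to the interaction count.

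| Centres | Main effects (virologic / clinical) | With interactions (virologic / clinical) |
|---|---|---|
| 3 | 8 / 9 | 18 / 21 |
| 6 | 11 / 12 | 27 / 30 |

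For 68 patients, 18 to 30 parameters leave about 2 to 4 patients each (68/30 = 2.3; 68/18 = 3.8). In simulations with assumed status mixes (300 trials per setting), the interaction model had no finite maximum-likelihood fit in 70–98% of trials with 2–3 centres and in all trials with 6. The main-effects model failed in 0–13% and 5–24%. Exact fits were not simulated.

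**The case against.** The strongest reply is that the documents already hold a coherent rule. Section 8.4 is the dedicated multiplicity section and 4.1.2 agrees with it. Section 14.1.1 does not say that Bonferroni is for doses only. The protocol prints 2.69640 for the final analysis, and section 18 does not withdraw it. On that reading error stays well below 2.5% and 14.1.1 is merely loosely worded. Much of this stands: a reader might infer that the trial would breach its alpha limit, but that follows only if 14.1.1 overrides both 8.4 and the protocol boundary. What remains is that the operative paragraph says something different and the SAP gives no number.

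It can also be said that reporting Type III p-values does not make them the deciding test, since the odds ratios and intervals show direction. That is fair, but no other p-value is defined for the primary analysis, and the 95% intervals are not tied to any adjusted level.

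On the model, Table 3 is a summary, and SAP 8.1, where "the following factors/covariates will be considered in the Binary Logistic regression and Repeated Measures Logistic regression model", defers to 14.1, so 8.1 adds little. Table 3 and the protocol still list no interactions. Two stronger readings should be resisted. A reader might infer that a dose effect is undefined once interactions are present. When the cells are estimable, an averaged contrast exists; it depends on weights that the SAP does not state. A reader might also infer that significance-based removal would in practice choose the primary model. It comes only after the exact step, and how often it would be reached has not been shown.

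**Conclusion.** The conflict is real and sits in the decision rule itself. The prescribed p-values test none of the four stated hypotheses, the Bonferroni sentence contradicts 8.4 and 4.1.2, and the primary model contains interactions that Table 3 and the protocol do not list and section 18 does not declare.

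If 14.1.1 were followed rather than 8.4, familywise one-sided error would be about 3.3–4.6% in normal theory, and between 2.7% (Wald) and 4.2–4.5% (pooled z) unadjusted at 68 patients, against 2.5%. The choice between the two sentences changes the verdict in about 11–15% of trials at the planned effects. The figures rest on near-equal arms, no missing outcomes and assumed endpoint correlations; the adjusted-model figures also rest on an assumed number of centres and covariate mix. The interaction model makes the fallbacks likely to be needed, at a frequency that cannot be fixed from the documents.

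Keeping 2.69640 without an interim would not be an error. It is conservative, and the SAP only needs to say whether it applies.

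**What to change.** Before unblinding:

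- (a) Base the decision on four 1-df one-sided dose-versus-placebo contrasts from the main-effects logistic model of Table 3. Report the Type III test as descriptive.
- (b) Replace the Bonferroni sentence in 14.1.1 with the four-way adjustment of 8.4.
- (c) Print one critical value. Either keep 2.69640 and call it conservative because no interim is done, or use 0.00625 one-sided (z > 2.498) and note that its small-sample error can reach about 2.5–2.9%. Give decision intervals at the matching level (98.75% two-sided for 0.00625) and keep the 95% intervals as descriptive.
- (d) Move the treatment interactions to 8.5 as exploratory.
- (e) Replace removal by statistical significance with a fixed, pre-specified order of dropping terms. The main-effects model can also fail to fit, so this is needed in any case. Apply the same level and direction to the exact-logistic and Fisher fallbacks, each dose against placebo.
- (f) List these changes in section 18.

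The cost is SAP wording and contrast statements, with no further patients or data. Decision intervals become wider than 95%.
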